### 4.2. SECONDARY EFFICACY ENDPOINTS

#### 4.2.1. Hierarchical Secondary Endpoints

- 1) Mean absolute change from baseline FVC (L)\* over 26 weeks.
- 2) Time to first protocol defined pulmonary exacerbation (PDPE)\*\* of any grade over the 26-week treatment period as recorded on the CRF. This is the time in days and is defined as:

$$\text{Time} = (\text{date of PDPE}) - (\text{date of Trial Day 1}) + 1$$

Trial Day 1 is defined in Section 6.2.2.

A PDPE occurs when subjects are treated with IV antibiotics for four or more of the following twelve signs or symptoms:

\*Updated in this SAP to be reported in L rather than mL to match the units used in data collection (see Section 11).

\*\*Clarified in this SAP that pulmonary exacerbations classified as protocol defined pulmonary exacerbations (PDPEs) will be used in the main analyses for these endpoints (see Section 11).

## Statistical Analysis Plan

- Change in sputum production (volume, color, consistency).
- Increased dyspnea.
- New or increased hemoptysis.
- Malaise, fatigue, or lethargy.
- Fever ( $\geq 38$  °C).
- Anorexia or weight loss.
- Sinus pain or tenderness.
- Change in sinus discharge.
- FVC or FEV1 decreased by >10% from previous recorded value.
- Radiographic signs indicative of pulmonary infection.
- Increased cough.
- Changes in physical examination of the chest.

PDPEs will be identified from the pulmonary exacerbation (PE) Review CRF page, where IV antibiotics were recorded as being given for a PE and, in addition, 4 or more of the above signs or symptoms were ticked.

Time to first PE will also be calculated, in a similar manner, and explored under this endpoint, however the hierarchical testing will be based on time to first PDPE. A PE is defined as any event recorded on the PE Review CRF page that has associated antibiotic use (oral, inhaled, or IV), whether or not it meets the above conditions.

- 3) Number of days on antibiotics (oral, inhaled, or IV) due to PDPE\*\* over the 26-week treatment period. Medication use for a PE will be identified on the concomitant medication page by a yes/no box; a further check will be made to ensure medications are for a PDPE (i.e. that the PE event to which the medication is linked satisfies the above criteria for a PDPE). It will also be checked that both the PDPE and the medication use started on or after Trial Day 1 (defined in Section 6.2.2). Antibiotics are identified by their Anatomical Therapeutic Chemical (ATC) Level 2 code J01 (antibacterials for systemic use).

Number of days on one antibiotic = stop date-start date+1

The number of days for all occurrences will be summed. If multiple antibiotics are received for the same event, the durations will be computed separately and added together. If an antibiotic is ongoing at the end of the subject's participation in the trial, the subject's date of last participation in the trial will be used in the calculation instead of the stop date.

Date of last participation in the trial is defined in Section 6.2.5.

\*Updated in this SAP to be reported in L rather than mL to match the units used in data collection (see Section 11).

\*\*Clarified in this SAP that pulmonary exacerbations classified as protocol defined pulmonary exacerbations (PDPEs) will be used in the main analyses for these endpoints (see Section 11).

## Statistical Analysis Plan

As a supportive analysis, the following endpoints will be calculated:

- Number of distinct days on antibiotics due to PDPE over the 26-week treatment period: if multiple antibiotics are received for the same event and overlap (i.e. stop date of one antibiotic  $\geq$  start date of next antibiotic), days with more than one antibiotic will be counted only once.

Number of distinct days on antibiotics = sum(days with at least one antibiotic intake for an event).

If an antibiotic is ongoing at the end of the subject's participation in the trial, days will be counted up until the subject's date of last participation in the trial.

- Number of days on antibiotics (oral, inhaled, or IV) due to PE over the 26-week treatment period.
- Number of distinct days on antibiotics due to PE over the 26-week treatment period.

As supportive information, the following variables will be calculated:

- Number of distinct episodes of use of antibiotics due to PDPE, defined as any recorded use of antibiotics due to PDPE with a different start date from any other recorded use of antibiotics due to PDPE.
- Number of courses of antibiotics due to PDPE, defined as any recorded use of antibiotics due to PDPE with a start date 14 or more days after the stop date of all previous antibiotics for any PDPE.

All subjects experiencing a PDPE would have received IV antibiotics.

These supportive endpoints/variables will not be part of the hierarchical testing.

- 4) Number of days in hospital (admissions only) due to PDPE\*\* over the 26-week treatment period. For each hospital admission, the number of days in hospital will be calculated as (end date)-(start date)+1. Each hospitalization with a reason of PE will be cross-referenced with a PE from the PE Review CRF page to determine if the hospitalization was due to a PDPE. If the start date of the hospitalization is included within the dates of any PDPE for that subject, then that hospitalization will be designated as due to PDPE. If the hospitalization is ongoing at the end of the subject's participation in the trial, the subject's date of last participation in the

\*Updated in this SAP to be reported in L rather than mL to match the units used in data collection (see Section 11).

\*\*Clarified in this SAP that pulmonary exacerbations classified as protocol defined pulmonary exacerbations (PDPEs) will be used in the main analyses for these endpoints (see Section 11).

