## Statistical Analysis Plan

trial will be used in the calculation instead of the end date.

As a supportive analysis, the following endpoint will be calculated:

- Number of days in hospital (admissions only) due to PE.

The hierarchical testing will be based on days in hospital due to PDPE.

- 5) Rate of PDPE\*\* (per person year) over the 26-week treatment period.

The overall rate of PDPE (per person year) over the 26-week treatment period will be calculated for each treatment group as:

$$\text{Overall Rate} = \text{total number of PDPE} / \text{total follow-up duration}$$

where total follow-up duration (years) =  $([\text{last participation date}] - [\text{date of Trial Day 1}] + 1) / 365.25$  summed over all subjects in the treatment group.

Trial Day 1 is defined in Section 6.2.2.

Date of last dose of trial medication is defined in Section 6.2.1.

In the above calculations, rate will be rounded to two decimal places for displaying purposes.

The overall rate of PE (per person year) over the 26-week treatment period will also be calculated, in a similar manner, and explored under this endpoint, however the hierarchical testing will be based on the rate of PDPE.

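### Hospital days due to PDPE: the only stated attribution test is the admission date, so a PDPE start recorded after admission drops the whole stay from a gated endpoint

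*SAP*

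**What the plan says.** SAP 4.2.1 item 4 defines the endpoint as "Number of days in hospital (admissions only) due to PDPE" over the treatment period. The length of each stay is fixed: "For each hospital admission, the number of days in hospital will be calculated as (end date)-(start date)+1". Attribution then has two steps.

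- First, a filter and look-up: "Each hospitalization with a reason of PE will be cross-referenced with a PE from the PE Review CRF page".
- Second, the criterion: "If the start date of the hospitalization is included within the dates of any PDPE for that subject". Where it is met, the entire stay is classed as a PDPE stay.

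No overlap test, tolerance, record link or adjudication step is given there or in SAP 8.2.4. Protocol 10.2.7.1, objective 4, contains no attribution rule.

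On its role, the SAP says: "The hierarchical testing will be based on days in hospital due to PDPE". SAP 8.2.4 fits a negative binomial model without imputation and requires p below 0.05 before the next endpoint, the PDPE rate, is tested. Hospital days due to any PE are a supportive analysis outside the hierarchy.

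Two neighbouring items matter. Item 2 defines the event: "A PDPE occurs when subjects are treated with IV antibiotics for four or more of the following twelve signs or symptoms". Item 3 attributes antibiotic days through a record link, by checking "that the PE event to which the medication is linked satisfies the above criteria for a PDPE". It also requires both event and medication to start on or after Trial Day 1, but not that the medication date fall inside the PDPE's dates.

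**The concern.** The criterion looks at a single day of the stay. If that day is outside the PDPE's recorded dates, no day of the stay counts; if it is inside, every day counts. The outcome therefore depends on how the site dated the start of the event, which the visible text leaves undefined. A PDPE requires intravenous antibiotics, and these may begin the day after admission. A site that dates the event from the first dose would place the admission just before it.

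The antibiotic days for that same event would be kept, because item 3 works through the record link. The hospital days would become zero. Misclassification of this kind adds noise to an endpoint that stands between the earlier tests and the PDPE rate.

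**Working it through.** The documents state no figure for this endpoint, so there is none to reproduce. The check applies the rule literally.

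**Inputs.** Admission date *a* and discharge date *d* (SAP 4.2.1 item 4), and PDPE start *s* and end *e* (PE Review page of the CRF). Stay lengths of 7, 10 and 14 days are assumed for illustration; the documents give none.

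**Formulas.**

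- Rule as written: days counted = *d* − *a* + 1 if *s* ≤ *a* ≤ *e*, otherwise 0.
- Days of the stay inside the PDPE: min(*d*, *e*) − max(*a*, *s*) + 1, or 0 if negative.
- Any-overlap rule: days counted = *d* − *a* + 1 if *a* ≤ *e* and *d* ≥ *s*, otherwise 0.

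**A 14-day stay.** Set *a* = 1 and *d* = 14, so the length is 14 − 1 + 1 = 14. In the first four rows the PDPE ends after discharge; in the last two it starts before admission.

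| PDPE dates relative to the stay | Counted as written | Days inside the PDPE | Counted under any-overlap |
|---|---|---|---|
| Starts 3 days before admission | 14 | 14 | 14 |
| Starts on admission day (*s* = 1) | 14 | 14 | 14 |
| Starts 1 day after admission (*s* = 2) | 0 | 14 − 2 + 1 = 13 | 14 |
| Starts 2 days after admission (*s* = 3) | 0 | 14 − 3 + 1 = 12 | 14 |
| Ends on admission day (*e* = 1) | 14 | 1 − 1 + 1 = 1 | 14 |
| Ends the day before admission (*e* = 0) | 0 | 0 | 0 |

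**Shorter stays, PDPE start one day after admission.** For 7 days, 0 are counted and 6 lie inside. For 10 days, 0 are counted and 9 lie inside. Any-overlap counts 7 and 10.

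The third and fifth rows show the difficulty. A stay with 13 days inside the PDPE scores 0, while one with a single day inside scores 14. The rule is thus not a stricter measure of time in hospital during a PDPE. The first row marks its limit: when the PDPE began several days before admission, a one-day dating error changes nothing.

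**The case against.** **The dating mechanism is assumed.** Under SAP 4.2.1, intravenous use and the ticked signs classify an event on the PE Review page; nothing says they date it. Protocol 6.1 distinguishes the end of treatment for an exacerbation from the end of the adverse event. An event dated from symptom onset would normally begin on or before the admission it caused. This stands: late dating is possible but not shown. It cannot be excluded either, since the start date is undefined.

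**The SAP says if, not only if.** This is correct, and exclusivity is an inference. It rests on this being the only criterion offered for the step.

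**Data checks may catch it.** Protocol 13.2 provides for queries on inconsistencies, and Protocol 8.2.1.6 records hospital dates on both the CRF and the follow-up SAE form. These help, but no check is named for this pair of dates. SAP 6.3 deals with missing or partial dates, not complete dates that disagree. The redacted SAP appendices may say more.

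**The any-PE analysis keeps these stays.** It does, with the same model (SAP 8.2.4.1). It also admits stays for events that are not PDPEs and lies outside the hierarchy, so it mitigates without repairing the tested endpoint.

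**Requiring the PDPE to be present at admission is a defensible sense of causation.** That is fair as a principle, but it works only if the recorded start reflects when the event began.

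**Stronger readings a reader might infer.** One is that endpoints 3 and 4 contradict each other on whether a PDPE occurred. They do not: endpoint 4 counts inpatient days only, and Protocol 8.2.1.4 excludes hospital-in-the-home care and emergency attendance, so antibiotic days with no hospital days are an ordinary result. Others are that a particular share of PDPE days is lost, or that one arm is favoured. The documents give no mismatch frequency, and the rule is identical in both arms.

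**Conclusion.** The point holds as a boundary defect in a stated rule. Per affected stay the effect is total: the full length becomes 0, which in the assumed 14-day example means 14 days become 0 with 13 of them inside the PDPE. Across the trial, the number of affected stays and the effect on the rate ratio or power cannot be calculated from the documents.

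The conclusion rests on two assumptions: that the admission-date criterion is the only route to attribution, and that some sites may record a PDPE start later than the admission. No directional bias is shown. It would be a cheap improvement to an endpoint that gates the PDPE rate; nothing here shows that the endpoint is invalid.

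**What to change.** Before unblinding, change the criterion in SAP 4.2.1 item 4: a hospitalization recorded with reason PE is due to PDPE if any day from admission to discharge overlaps the start-to-end dates of a PDPE for that subject. In programming terms, replace *s* ≤ *a* ≤ *e* with *a* ≤ *e* and *d* ≥ *s*. Keep the PE-reason filter, the length formula and the existing use of the last participation date for ongoing stays.

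The cost is one phrase and one date condition, on dates already collected. The downside is small: a PE stay in which a PDPE is recorded only late in the admission counts in full. The present rule already counts days outside the PDPE when admission falls near its end.

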## Statistical Analysis Plan

trial will be used in the calculation instead of the end date.

As a supportive analysis, the following endpoint will be calculated:

- Number of days in hospital (admissions only) due to PE.

The hierarchical testing will be based on days in hospital due to PDPE.

- 5) Rate of PDPE\*\* (per person year) over the 26-week treatment period.

The overall rate of PDPE (per person year) over the 26-week treatment period will be calculated for each treatment group as:

$$\text{Overall Rate} = \text{total number of PDPE} / \text{total follow-up duration}$$

where total follow-up duration (years) =  $([\text{last participation date}] - [\text{date of Trial Day 1}] + 1) / 365.25$  summed over all subjects in the treatment group.

Trial Day 1 is defined in Section 6.2.2.

Date of last dose of trial medication is defined in Section 6.2.1.

In the above calculations, rate will be rounded to two decimal places for displaying purposes.

The overall rate of PE (per person year) over the 26-week treatment period will also be calculated, in a similar manner, and explored under this endpoint, however the hierarchical testing will be based on the rate of PDPE.

### 4.2.2. Non-hierarchical Secondary Endpoints

- 1) Incidence of PDPEs\*\* (yes or no, binary outcome) over the 26-week treatment period.

Incidence of PEs (yes or no, binary outcome) over the 26-week treatment period will also be explored under this endpoint, however the main focus will be on the incidence of PDPEs.

- 2) Ease of expectoration measured at Weeks 6, 14 and 26 using the absolute change from baseline visual analogue scale (VAS) score.

\*Updated in this SAP to be reported in L rather than mL to match the units used in data collection (see Section 11).

\*\*Clarified in this SAP that pulmonary exacerbations classified as protocol defined pulmonary exacerbations (PDPEs) will be used in the main analyses for these endpoints (see Section 11).

Pharmaxis Ltd

DPM-CF-303

Final v1.0

## Statistical Analysis Plan

- 3) Mean absolute change from baseline CFQ-R respiratory domain score measured at Weeks 6, 14 and 26. This will be appropriately transformed according to the scoring manual, so that the best response will be uniformly the highest score and the worst response will be uniformly the lowest score. More details are provided in [REDACTED]

The CFQ-R respiratory domain includes the Question 42 (CRF Question 3), “Have you had to cough up mucus?” The scoring algorithm scores an affirmative answer to this question as a negative outcome for the subject, however, due to the mechanism of action of mannitol (i.e. inducing coughing up mucus) an affirmative answer here may not be a negative outcome and hence this question is inappropriate here. Therefore, the endpoint will also be derived omitting this question.

### 4.3. SAFETY ENDPOINTS

Safety endpoints include adverse events (AEs; including deaths), extent of trial medication exposure and trial medication compliance, vital signs, and physical examination data.

\*Updated in this SAP to be reported in L rather than mL to match the units used in data collection (see Section 11).

\*\*Clarified in this SAP that pulmonary exacerbations classified as protocol defined pulmonary exacerbations (PDPEs) will be used in the main analyses for these endpoints (see Section 11).

## Statistical Analysis Plan

### 5. ANALYSIS SETS

#### 5.1. SAFETY SET

The Safety (SAF) set will include all subjects who were administered at least one dose (or part thereof) of randomized trial medication. Subjects will be analyzed according to trial medication received. The SAF set will be used for all analyses of safety endpoints.

#### 5.2. INTENT-TO-TREAT SET

The Intent-to-Treat (ITT) set will include all randomized subjects. Subjects will be analyzed according to randomized trial medication. The ITT set will be used for all analyses of efficacy endpoints.

#### 5.3. PER PROTOCOL SET

The Per Protocol (PP) set consists of all randomized subjects, excluding those who had deviations from the protocol that may affect the assessment of response to trial medication. The criteria for exclusion from the PP are defined in Section 5.5.

#### 5.4. MANNITOL TOLERANCE TEST SET

The MTT set will include all subjects participating in the MTT prior to randomization regardless of their subsequent randomization status. It will include subjects who fail the MTT (MTT positive) or who have an incomplete procedure, along with those who pass the MTT (MTT negative). If subject is re-screened, only the re-screen subject number will be included in the MTT set, the original subject number will be excluded.

#### 5.5. PROTOCOL DEVIATIONS

Protocol deviations identified by the clinical research associates during their monitoring visits were captured in [REDACTED] using broad category groupings.

All recorded protocol deviations were reviewed during the course of the trial. In addition, protocol deviations were identified through programmatic checks in order to assist in the assignment of subjects to the PP set. At the BDRM, held prior to the unblinding of the trial deviations were grouped into subcategories under each broad category grouping and decisions were made on whether to exclude each subject from the PP set by categorizing each recorded and programmed protocol deviation as major or minor, where major identifies a reason for exclusion from the PP set.

Pharmaxis Ltd

DPM-CF-303

Final v1.0

## Statistical Analysis Plan

All major protocol deviations, from [REDACTED] and programmed, will be listed and summarized for the ITT set based on the [REDACTED] category and assigned subcategory. Important minor protocol deviations, including those related to trial inclusion or exclusion criteria, conduct of the trial, subject management or subject assessments, were identified at the BDRM and will be listed by [REDACTED] category and assigned subcategory.

Criteria to determine if a subject will be included in the PP set were detailed in a BDRM preparation plan together with details of the programmatic listings to be prepared. The adjusted criteria confirmed during the BDRM to determine if a subject will be excluded from the PP set were:

- Did not meet all the inclusion and exclusion criteria.
- Was randomized but did not take at least one dose of trial medication.
- Compliance to trial medication while taking trial medication <60%.
- No valid baseline FEV1 measure, where a baseline measure was considered non valid if precluded medications were not withheld as detailed in the protocol.
- Started treatment with maintenance hypertonic saline where it was considered that there was a potential for efficacy assessments to be impacted.
- Started or stopped treatment with rhDNase or maintenance antibiotics where it was considered that there was a potential for efficacy assessments to be impacted.

Further details of the rules applied to determine inclusion in the PP set will be documented in the BDRM Highlights and will be agreed and finalized prior to database lock.

Only FEV1 measurements taken in the absence of precluded medications will be considered valid. Precluded medications and required withholding periods are detailed in Table 3 (as detailed in the protocol and CRF).

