- Premedicate with four puffs of albuterol/salbutamol from a metered dose inhaler (MDI) (360-400µg), 5 to 15 minutes prior to each dose of IMP. The subject's preferred bronchodilator may be used as an alternative premedication. Care must be taken to ensure that a bronchodilator is used prior to ALL doses of IMP;
- Administer dose of IMP (mannitol/control) according to 'IMP Administration Procedure' (see Section 6.1 figure 2) and randomization number. Check the subject's inhalation technique and re-train if required;
- Perform pulmonary function test 30 minutes post dose. If the subject has a measured fall in FEV₁ >20% at 30 minutes post dose completion, no further study medication should be administered. The subject should be continued in the study on an intention to treat basis. Symptomatic bronchoconstriction should be managed as medically appropriate);
- Conduct drug accountability; *and*
- Access IWRS to complete the required visit information.

8.1.2.5 📞 Phone call 2 weeks after visit 2 (Week 8 ± 3 days)

Two weeks after visit 2, the Investigator or designate, will telephone the subject, and complete the procedures as per Section 8.1.2.2.

8.1.2.6 📞 Phone call 2 weeks before visit 3 (Week 12 ± 3 days)

Two weeks before visit 3, the Investigator or designate will telephone the subject. Information collected will be as per Section 8.1.2.3.

8.1.2.7 Visit 3

Visit 3 should occur at the end of 14 weeks trial treatment (± 7 days)

Prior to the visit, confirm medication-withholding periods have been adhered to. If not, the subject's visit should be postponed.

The following procedures will be performed:

- Review subject diary.
- Review concomitant medications and adverse events (including pulmonary exacerbations or hemoptysis);
- Complete ease of expectoration VAS and respiratory domain of the CFQ-R questionnaire;
- Conduct physical examination (chest sounds, weight, BP, HR, O₂ saturation, temperature, respiratory rate);
- Perform pre-mannitol pulmonary function testing (FEV₁, FVC, PEF, FEF₂₅₋₇₅);
- Dispense IMP and bronchodilator according to randomization schedule;
- Premedicate with four puffs of albuterol/salbutamol from a metered dose inhaler (MDI) (360-400µg), 5 to 15 minutes prior to each dose of IMP. The subject's preferred bronchodilator may be used as an alternative premedication. Care must be taken to ensure that a bronchodilator is used prior to ALL doses of IMP;

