10.1.2.2 Per protocol (PP) analysis set

The per protocol analysis set consists of all randomized subjects, who have:

- Strictly met all the inclusion and exclusion criteria (i.e. will exclude those subjects who have been granted an exception to be included in the trial);
- No major protocol deviations which would affect efficacy evaluations;
- Taken trial drug for at least 60% of the 26-week treatment period;
- A valid baseline FEV₁ measure; *and*
- At least two valid assessments of FEV₁ following the baseline visit (Visit 0).

The decision to include subjects in the per protocol dataset will be made prior to unblinding of the randomization schedule. For the per protocol analysis any non-valid assessments of FEV₁ will be excluded from the analysis. The validity of the FEV₁ measurements will be assessed prior to unblinding. The subject must meet the requirement for a valid baseline and two valid post-baseline FEV₁ assessments.

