10.2.6 Primary per protocol analysis

The primary analysis is planned to estimate the treatment effect of being *randomized to mannitol*. In order to estimate the treatment effect of *taking mannitol* a per protocol analysis is planned. This entails re-fitting the primary efficacy model to the per-protocol analysis set.

The results of this per protocol analysis will provide an extra robustness check on the main results from the ITT population.

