#### For Efficacy data:

- On-treatment period: period of time while the subject is on trial medication; it starts with the first intake of trial medication after randomization and ends 7 days after the last trial medication intake.
- Off-treatment period: period of time while the subject is not on trial medication; it starts the eighth day after the last trial medication intake and ends on the date of last participation in the trial.

All efficacy analyses will be conducted considering all measurements collected (i.e. including both on-treatment and off-treatment period data).

In addition, for the primary endpoint, supportive analyses will be conducted considering only measurements collected during the on-treatment period.

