## Statistical Analysis Plan

### 6.3. MISSING DATA

Missing or partial dates will be resolved in the most conservative manner. Additional details regarding partial or missing dates for the different safety data are given in Sections 6.2.1, 7 and 9 where applicable.

Details of imputation of missing values for efficacy endpoints are given in Section 8. Subjects who discontinue trial medication should remain in the trial and continue to provide all scheduled measurements. While all efforts will be made to ensure subjects remain in the trial, the following planned imputation strategy will allow for appropriate analyses of FEV1, FVC, ease of expectoration VAS score, and CFQ-R respiratory domain in the presence of missing data.

To calculate baseline values, missing Visit 1 measurements will be replaced by Visit 0 (screening) measurements, if available.

Missing post-baseline measurements as a result of withdrawal from the trial will be imputed in both ITT and PP analyses using an imputation using dropout reason (IUDR) methodology. For subjects who withdraw from the trial due to AE, death, physician decision, or lack of efficacy, missing post-baseline measures as a result of withdrawal from the trial will be imputed using the baseline measurement (baseline observation carried forward [BOCF] procedure). Missing measurements as a result of other causes of withdrawal from the trial (i.e. lost to follow-up, relocation, pregnancy, major protocol deviation, sponsor decision, withdrawal of consent, or other) will not be imputed. Missing data at intermediate visits (i.e. where data is available at a later visit) will not be imputed. Any measurements excluded from the PP analysis at the BDRM, and any derived variables based on these excluded measurements, will be treated as missing data but will not be included in the imputation process.

Imputation of missing FEV1 measurements by means of BOCF is a reasonable assumption in studies of adult subjects with CF, as those subjects who withdraw from the trial will no longer receive trial medication and are thus likely to promptly return to their baseline lung function. Imputation by BOCF specifically inhibits any assumed prolongation of an observed early trial medication benefit implicitly conferred by a mixed model.

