#### 9.2. TRIAL MEDICATION COMPLIANCE

Trial medication compliance (%) will be summarized for the SAF set using summary statistics for continuous variables. Compliance to trial medication while taking trial medication will be calculated based on the subject reported last date of trial medication as follows:

$$\text{Compliance} = 100\% \times \frac{\sum_{i=1}^3 (D_i) - \sum_{i=2}^4 (R_i)}{2 \times 10 \times ([\text{last date of trial med}^*] - [\text{date of Trial Day 1}] + 1)}$$

\* Date of last dose of trial medication is as defined in Section 6.2.1

where:

$D_i$  = number of capsules dispensed at Visit  $i$ .

$R_i$  = number of unused capsules returned at Visit  $i$ .

Pharmaxis Ltd

DPM-CF-303

Final v1.0

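### The SAP measures per-protocol compliance only up to the last dose, so early stoppers whom the protocol would exclude can stay in the PP set and dilute one supportive estimate

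*SAP*

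**What the plan says.** Protocol 10.2.6 separates the effect of being randomized to mannitol from the effect of taking it, and for the latter "a per protocol analysis is planned". Two of the membership rules in Protocol 10.1.2.2 matter here. The exposure rule is "Taken trial drug for at least 60% of the 26-week treatment period". The data rule is "The subject must meet the requirement for a valid baseline and two valid post-baseline" FEV1 assessments.

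The list in SAP 5.5, presented as the criteria confirmed at the blind data review meeting (BDRM), has a different exposure rule: exclusion for "Compliance to trial medication while taking trial medication <60" per cent. SAP 9.2 fixes the denominator: "Compliance to trial medication while taking trial medication will be calculated based on the subject reported last date of trial medication". Beyond at least one dose, the list sets no minimum time on drug and no minimum number of valid post-baseline FEV1 values. SAP 5.5 also says that a visit with invalid spirometry is dropped without removing the subject.

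Supportive Analysis 1 (SAP 8.1.3.1) refits the primary model on this set. SAP 6.2.7 states: "All efficacy analyses will be conducted considering all measurements collected (i.e. including both on-treatment and off-treatment period data", and Table 6 marks off-medication data as included for this analysis. Under SAP 6.3, values missing after trial withdrawal for certain reasons "will be imputed in both ITT and PP analyses" from baseline (BOCF).

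SAP 11 item 3 records that the PP criteria were adjusted and describes the handling of invalid visits. It mentions neither the exposure rule nor the two-value rule.

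**The concern.** A compliance ratio that ends at the last dose measures how well a subject dosed while dosing. It does not measure how much of the trial was spent on drug. Someone who doses perfectly for a few weeks and stops passes the SAP rule but fails the protocol rule.

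The protocol creates such subjects by design. A fall in FEV1 of more than 20% after the clinic dose at Visit 1, 2 or 3 ends study drug, and "The subject should be continued in the study on an intention to treat basis" (Protocol 8.1.2.1, repeated for Visits 2 and 3). Protocol 9.2 also asks sites to keep all other drug discontinuers in the trial.

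The SAP offers the PP analysis as an additional check on the ITT result. If it retains early stoppers with the same off-drug or baseline-carried values as the primary analysis, agreement between the two says little about the effect of taking mannitol.

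**Working it through.** The point disputes no stated figure. The 80 mL used below is the planning difference in Protocol 10.1.1. That calculation reproduces: with SD 230 mL and two-sided 5%, a t-test needs 174.7 per arm for 90% power, and 175 per arm gives 90.05%.

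**Inputs.** The treatment period is 26 × 7 = 182 days. Target days for Weeks 6, 14 and 26 are 43, 99 and 183 (SAP Table 4). Dosing is 10 capsules per administration and 20 per day (SAP 9.2). The on-treatment period ends 7 days after the last dose (SAP 6.2.7). The three visits have equal weight (SAP 8.1.1).

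**Step 1: what the protocol rule allowed.** 0.60 × 182 = 109.2, so about 110 days on drug. Week 14 falls on Day 99, at latest Day 106 within its ±7-day window. With continuous dosing, a subject meeting the rule could therefore be off drug only at Week 26.

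**Step 2: the two rules applied to the same subjects.** SAP compliance is capsules used ÷ (20 × days from randomization to last dose). Every dose is assumed taken. For the Visit 2 and Visit 3 stops, the last dose is the single one given in clinic.

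| Last dose | Protocol exposure | SAP compliance | Days off drug at later visits |
|---|---|---|---|
| Day 14 | 14/182 = 7.7%, excluded | 280/280 = 100%, passes | Week 14: 99 − 14 = 85; Week 26: 183 − 14 = 169 |
| Visit 2, Day 43 | 43/182 = 23.6%, excluded | (42 × 20 + 10)/(43 × 20) = 850/860 = 98.8%, passes | Week 14: 99 − 43 = 56; Week 26: 183 − 43 = 140 |
| Visit 3, Day 99 | 99/182 = 54.4%, excluded | (98 × 20 + 10)/(99 × 20) = 1970/1980 = 99.5%, passes | Week 26: 183 − 99 = 84 |

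For the Visit 2 stopper, a discontinuation visit within two weeks falls by Day 57. SAP Table 4 assigns it to Week 6 (Days 14 to 70), so it cannot replace the off-drug Week 14 value. Two of three equally weighted values are then off drug.

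**Step 3: possible dilution.** Let p be the share of mannitol PP subjects affected and v the number of visits lost to off-drug or BOCF values. Assume no change on control (the planning assumption) and full return to baseline (the SAP's own premise for BOCF). The effect shown is 80 × (1 − p × v/3) mL:

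| p | v = 1 | v = 2 | v = 3 |
|---|---|---|---|
| 5% | 78.7 | 77.3 | 76.0 |
| 10% | 77.3 | 74.7 | 72.0 |
| 20% | 74.7 | 69.3 | 64.0 |

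If only half the effect is lost, the formula becomes 80 × (1 − p × v/6). The range is then 80 × (1 − 0.05/6) = 79.3 mL to 80 × (1 − 0.20 × 3/6) = 72 mL.

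**The case against.** A reader might infer that the SAP introduced off-drug and BOCF values into the PP analysis. It did not. Protocol 10.2.6 refits the primary model, and Protocol 10.2.4 gives that model data after drug discontinuation as well as BOCF. A subject stopping at Day 110 would bring an off-drug Week 26 value under the protocol too. What changed is the limit on exposure, which had kept such values to Week 26 under continuous dosing.

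A reader might also infer that these subjects will certainly be in the PP set. The documents do not show that. SAP 5.5 leaves further rules to the BDRM Highlights, which are not available here, and individual deviations could be classed as major. A subject stopped after the very first clinic dose scores 10/20 = 50% and is excluded if all unused capsules come back.

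Nor is the trial without an on-drug estimate. Supportive Analyses 6 to 8 drop FEV1 values more than 7 days after discontinuation, and Supportive 8 imputes nothing. This covers part of the gap. However, these analyses run on the ITT set without the PP exclusions, and Supportive 6 and 7 still impute from baseline for some discontinuation reasons.

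The two-value rule is a separate omission and does not drive the exposure problem: a Visit 2 stopper who stays in the trial can have three valid values.

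Finally, a strict exposure rule has its own bias. SAP 8.1.1 cites higher drop-out on mannitol in the two earlier trials. If that recurs, the rule would remove more mannitol subjects and select those who tolerate the drug. This objection stands, and the fix has to allow for it.

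**Conclusion.** The point holds for one supportive analysis. The SAP's listed PP criteria replace the protocol's exposure rule with a weaker one and omit the two-value rule, and SAP 11 names neither change. On the listed criteria, a subject with 23.6% of the 26 weeks on drug is not excluded on exposure and can contribute two off-drug values out of three. Supportive Analysis 1 is then a poor estimate of the effect of taking mannitol, which is the purpose stated in Protocol 10.2.6.

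The likely direction is dilution. Its size cannot be determined because the documents give no discontinuation rate. The range of about 79 to 64 mL for a true 80 mL rests on the assumed 5% to 20% affected, one to three lost visits and full return to baseline. The gap from the protocol's own PP estimate would be smaller than the gap from 80 mL, because that estimate could also contain some off-drug or BOCF Week 26 values.

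It would be wrong to infer any effect on the primary result or the type I error. The primary analysis uses the ITT set, and the PP analysis is not part of the testing hierarchy.

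**What to change.** 1. In SAP 5.5, restore both protocol criteria: at least 60% of the full 26 weeks on drug, and two valid post-baseline FEV1 values that are observed, not imputed.
2. In Supportive Analysis 1, set FEV1 taken after the 7-day on-treatment limit to missing and apply no BOCF. In Table 6, change the imputation entry for this analysis to None and the off-medication entry to No, with matching edits in SAP 6.2.7, 6.3 and 8.1.3.1. This step goes beyond the protocol's refit of the primary model; the reason for it is the aim in Protocol 10.2.6.
3. In SAP 11 item 3, name each change from Protocol 10.1.2.2 and from the protocol's PP analysis that remains, with its reason.
4. Label the analysis as supportive, report PP exclusions by arm, and read it beside Supportive Analyses 6 to 8.

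The text changes are few, and the last-dose date and the on-treatment definition already exist (SAP 6.2.1 and 6.2.7). The cost is fewer subjects and values, a wider interval and possible selection of subjects who tolerate mannitol. The primary ITT analysis stays as it is.
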